5.6 Criteria for Taking a Participant Off Protocol Therapy

Duration of therapy will depend on individual response, evidence of disease progression and tolerance. In the absence of treatment delays due to adverse event(s), treatment may continue until one of the following criteria applies:

- Disease progression
- Intercurrent illness that prevents further administration of treatment
- Unacceptable adverse event(s)
- Participant demonstrates an inability or unwillingness to comply with the oral medication regimen and/or documentation requirements
- Participant decides to withdraw from the protocol therapy
- General or specific changes in the participant's condition render the participant unacceptable for further treatment in the judgment of the treating investigator

Participants will be removed from the protocol therapy when any of these criteria apply. The reason for removal from protocol therapy, and the date the participant was removed, must be documented in the case report form (CRF). Alternative care options will be discussed with the participant. No crossover from neratinib (Arm B) to neratinib plus fulvestrant (Arm A) will be allowed.

An ODQ Treatment Ended/Off Study Form will be filled out when a participant is removed from protocol therapy. This form can be found on the ODQ website or obtained from the ODQ registration staff.

In the event of unusual or life-threatening complications, treating investigators must immediately notify the Overall PI, [REDACTED]

5.7 Duration of Follow Up

Participants will be followed for up to 5 years after removal from protocol therapy or until death, whichever occurs first. During follow up, participants will be called every 6 months for survival assessment and to report any further anti-cancer treatment. Participants removed from protocol therapy for unacceptable adverse event(s) will be followed until resolution or stabilization of the adverse event.

5.8 Criteria for Taking a Participant Off Study

Participants will be removed from study when any of the following criteria apply:

- Lost to follow-up
- Withdrawal of consent for data submission
- Death

The reason for taking a participant off study, and the date the participant was removed, must be documented in the case report form (CRF).

For Centralized Subject Registrations, the research team submits a completed Off Treatment/Off Study form to ODQ when a participant comes off study. This form can be found on the ODQ website or obtained from the Coordinating Center.

6. DOSING DELAYS/DOSE MODIFICATIONS

General guidelines for dose delay and dose reduction are outlined below. Management guidelines for specific (e.g. diarrhea, pulmonary toxicity, hepatic toxicity,) and clinically-relevant toxicities are provided in Section 6.1. The dose delay and reduction instructions provided in these sections are intended to serve as guidelines to allow ongoing treatment for patients without signs or symptoms of progression while ensuring patient safety. In addition to the guidelines provided below, drug holds and dose reductions for the management of adverse events are permitted at the discretion of the treating physician.

The descriptions and grading scales found in the revised NCI Common Terminology Criteria for Adverse Events (CTCAE) version 4.0 will be utilized for dose delays and dose modifications. A copy of the CTCAE version 4.0 can be downloaded from the CTEP website http://ctep.cancer.gov/protocolDevelopment/electronic_applications/ctc.htm.

6.1 Neratinib dose modifications

Neratinib dose delays and modifications should be made as indicated in the following table(s). Dose re-escalation is not allowed after a dose reduction.

If significant treatment-related toxicities have not recovered to Grade ≤ 1 or baseline grade, the patient may skip up to 28 days from the last scheduled dose. Patients should be re-evaluated weekly during the delay whenever possible. In patients randomized to the fulvestrant arm (Arm A), fulvestrant dosing can continue while neratinib is held or if neratinib is discontinued, as long as the toxicity is felt to be unrelated to fulvestrant. Cycles will not be delayed in the event neratinib is held, but will resume as originally scheduled. The missed dose(s) will not be made up.

Dosing may also be suspended for up to 28 days for unanticipated intercurrent medical events that are not associated with study treatment toxicity or disease progression.

Dose Reduction Table

Dose Reduction Level	Neratinib Dose
Starting Dose	240mg, daily
Dose level -1	160mg, daily
Dose level -2	120mg, daily

If a patient develops a toxicity requiring a dose reduction below Dose level -2 (120mg), neratinib should be permanently discontinued.

6.1.1 General Toxicity

Guidelines for dose adjustments of neratinib for general toxicities that are clinically significant and felt to be drug related are shown in Table 1. For dose modifications for known toxicities (diarrhea, pulmonary toxicity, and hepatic toxicity) please see tables 2, 3, and 4.

Table 1: General Toxicities Requiring Dose Adjustment of Neratinib

NCI CTCAE v. 4.0	Action
Grade 2 adverse reaction*	
1st appearance	Hold neratinib until event resolves to Grade ≤ 1 ; then resume neratinib at the same dose level.
2nd appearance	Hold neratinib until event resolves to Grade ≤ 1 ; then resume neratinib at one dose level lower.
3rd appearance	Hold neratinib until event resolves to Grade ≤ 1 ; then resume neratinib at one additional dose level lower.
4th appearance	Discontinue neratinib permanently.
*Grade 2 ANC (neutrophil count decrease $\geq 1000/\mu\text{L}$), Grade 2 Anemia (Hemoglobin $< 10-8.0\text{g/dL}$), and Creatinine Clearance that is $\geq 50\text{ mL/min}$ (Grade 2 Chronic Kidney Disease is creatinine clearance $59-30\text{mL/min}$) are acceptable values for treatment as indicated in pre-treatment criteria, section 5.2. Do not hold neratinib for Grade 2 ANC, Grade 2 Anemia, or Creatinine Clearance that is $\geq 50\text{mL/min}$.	
Grade 3 adverse reaction	
1st appearance	Hold neratinib until event resolves to Grade ≤ 1 ; then resume neratinib at one dose level lower.
2nd appearance	Hold neratinib until event resolves to Grade ≤ 1 ; then resume neratinib at one additional dose level lower.
3rd appearance	Discontinue neratinib permanently.
Grade 4 adverse reaction	
1st appearance	Discontinue neratinib permanently

Based on National Cancer Institute Common Terminology Criteria for Adverse Events version 4.0 (NCI CTCAE v.4.0)

6.1.2 Gastrointestinal Toxicity:

Guidelines for adjusting doses of neratinib in the event of gastrointestinal toxicity of diarrhea are shown in Table 2. Refer to Section 5.3.3 for additional dietetic measures and pharmacological treatment.

Table 2: Gastrointestinal Toxicities Requiring Dose Adjustment of Neratinib

NCI CTCAE V4.0	Action

Grade 1 Diarrhea [Increase of <4 stools per day over baseline; mild increase in ostomy output compared to baseline.]
 
OR
 
Grade 2 Diarrhea [Increase of 4-6 stools per day over baseline; moderate increase in ostomy output compared to baseline;] lasting <5 days
 
OR
 
Grade 3 Diarrhea [Increase of ≥ 7 stools per day over baseline; incontinence; hospitalization indicated; severe increase in ostomy output compared to baseline limiting self-care activities of daily living (ADL);] lasting < 2 days
	
 • Continue neratinib at the current dose level. • Adjust anti-diarrheal treatment, as per the guidelines for management of diarrhea at the first onset of diarrhea. • Instruct patient to follow dietetic recommendations in the guidelines for management of diarrhea. • Fluid intake of ~2L/day should be maintained to avoid dehydration. • Once the event resolved to Grade ≤ 1 or baseline, start loperamide 4 mg with each subsequent neratinib administration

Persisting and intolerable Grade 2 Diarrhea lasting >5 days despite being treated with optimal medical therapy, or associated with fever, dehydration, or Grade 3-4 neutropenia
 
OR
 
Grade 3 Diarrhea lasting > 2 days despite being treated with optimal medical therapy, or associated with fever, dehydration, or Grade 3-4 neutropenia
 
OR
 
Any Grade 4 diarrhea [Life-threatening consequences; urgent intervention indicated]
	
 • Hold neratinib until recovery to Grade ≤ 1 or baseline. • Adjust anti-diarrheal treatment, as per the guidelines for management of diarrhea at the first onset of diarrhea. • Instruct patient to follow dietetic recommendations in the guidelines for management of diarrhea. • Fluid intake of ~2L should be maintained, intravenously if needed. • If recovery occurs: 
 • ≤ 1 week after withholding treatment, resume same dose of neratinib. • Within 1-3 weeks after withholding treatment, resume neratinib at one dose level lower. • If event occurs a 2nd time and the neratinib dose has not already been decreased, reduce neratinib dose to the next lower dose level. • If subsequent events occur, resume at an

NCI CTCAE V4.0	Action
	additional dose level lower once resolved to Grade \leq 1 or baseline 
 • Once the event resolved to Grade \leq 1 or baseline, start loperamide 4 mg with each subsequent neratinib administration

Based on National Cancer Institute Common Terminology Criteria for Adverse Events version 4.0

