5. TREATMENT PLAN

5.1 Treatment Regimen

Neratinib and fulvestrant will be administered in 4 week cycles, with 28 consecutive days defined as a treatment cycle. Treatment will be administered on an outpatient basis. There is no specific order of administration for neratinib and fulvestrant. Reported adverse events and potential risks are described in Section 7. Appropriate dose modifications are described in Section 6. No investigational or commercial agents or therapies other than those described below may be administered with the intent to treat the participant's malignancy.

Regimen Description					
Agent	Premedications; Precautions	Dose	Route	Schedule	Cycle Length
ARM A					
Neratinib	Loperamide and Colestipol (see Section 5.3.3)	240mg (six 40mg tablets)	Orally	Neratinib: once daily, continuous Loperamide: Days 1-28, continuous Colestipol: Days 1-28, continuous	28 days (4 weeks)
Fulvestrant		500mg (two injections of 250mg each)	Intramuscularly	Cycle 1: Day 1, 15 Cycle 2 and all subsequent cycles: Day 1	
ARM B					
Neratinib	Loperamide and Colestipol (see Section 5.3.3)	240mg (six 40mg tablets)	Orally	Neratinib: once daily, continuous Loperamide: Days 1-28, continuous Colestipol: Days 1-28, continuous	28 days (4 weeks)

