5.4 Agent Administration

5.4.1 Neratinib

Neratinib is administered orally once daily, continuously with no breaks, on days 1-28 of a 4-week (28-day) cycle, +/- 3 days. Neratinib is dosed as 240 mg once daily (six 40 mg tablets). Dosing is not weight-based. Patients should take neratinib at approximately the same time of day every day, preferably in the morning, with food. The dose is considered “missed” if not taken within approximately 12 hours of the usual administration time. Doses should not be retaken if skipped, missed, or vomited. Tablets must be swallowed whole; they may not be crushed, chewed, or dissolved.

Neratinib requires the use of anti-diarrheal prophylaxis with loperamide and colestipol (see Sections 5.3.3). Investigators must ensure that participants have loperamide and colestipol on hand when starting to take the investigational product. Loperamide and colestipol are the standard anti-diarrheal therapies in this study. If alternative anti-diarrheal medication is used, the reason must be documented in the source documents. Acceptable reasons are non-tolerance of standard therapies or lack of efficacy. Loperamide and colestipol will be dispensed directly by the site on day 1 of each cycle.

Dose modifications are delineated in section 6. If significant treatment-related toxicities have not recovered to Grade ≤ 1 or baseline grade, the patient may skip up to 28 days from the last scheduled dose. Patients should be re-evaluated weekly during the delay whenever possible. Patients randomized to the fulvestrant arm (Arm A) may continue

fulvestrant dosing while neratinib is held, as long as the toxicity is felt to be unrelated to fulvestrant.

Dosing may also be suspended for up to 28 days for unanticipated intercurrent medical events that are not associated with study treatment toxicity or disease progression.

Patients are to fill out a pill diary for every cycle (Appendix B) and return it to clinic staff at the end of each cycle.

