5.4.3 Mandatory Diarrhea Prophylaxis

Diarrhea is the major dose-limiting toxicity of neratinib, with onset typically occurring early in the course of treatment (during the first few days of the first cycle of treatment). Primary prophylactic use of antidiarrheal medication is mandatory for all patients taking neratinib. Loperamide and colestipol are the required standard therapies to treat diarrhea. Second-line antidiarrheal treatments and adjunctive therapies (i.e., octreotide [SANDOSTATIN®]) (or equivalent)) are also recommended for use when appropriate. The Investigator must review with the patient the Patient Instructions for the management of diarrhea in Appendix C.

The patient should be given clear instructions to contact the Investigator in the event of persistent Grade ≥ 2 diarrhea to discuss the appropriate course of treatment. Loperamide and colestipol should be dispensed directly with neratinib. It is very important to initiate treatment with loperamide and colestipol concomitantly with the first dose of neratinib to minimize occurrence and severity of diarrhea.

Refer to protocol Section 6.1.2, Table 2 for Dose Adjustment of Neratinib as applicable.

The Investigator or suitably trained and qualified delegate (e.g., MD, RN, NP, etc.) must

contact the patient by phone on Cycle 1 Day 2, Cycle 1 Day 3, and Cycle 1 Day 4 after the first dose of neratinib to inquire about compliance with loperamide and colestipol, diarrhea or any other adverse events. (These phone calls are very important and should be recorded in the clinical records together with response from the patient and action taken.)

Patients should be instructed to promptly report diarrhea symptoms and to report the number of stools per day and the dose of any anti-diarrheal medication taken each day for the first 28 days of therapy.

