5.4.3.1 Loperamide (Imodium ®)

For the first 14 days, loperamide 4 mg (2 tablets/capsules) will be self-administered orally 3 times a day (total 12 mg a day). The initial dose of loperamide will be administered orally with the first dose of neratinib. After the first 14 days, loperamide 4 mg (2 tablets/capsules) will be administered orally twice a day (total 8 mg a day) through the first cycle of therapy (Day 28) from start of neratinib dosing, whether the patient is experiencing diarrhea or not. Thereafter, loperamide will be administered as needed (not to exceed 16 mg per day) per the investigator's discretion. Commercial supply of loperamide will be used and provided by research pharmacies (cost covered by ██████████)

Loperamide Dosing

Day	Loperamide Dose
1-14	Daily dose of 12 mg in 3 divided doses of 4 mg
15-28	Daily dose of 8 mg in 2 divided doses of 4 mg
>28	Daily dose as needed (not to exceed 16 mg per day)

Loperamide Dose Adjustment

Patients are expected to take loperamide prophylaxis as directed. However, patients may require individualization of loperamide prophylaxis dose (up to a maximum dose of 16 mg per day) with the goal of titrating to 1-2 bowel movements a day.

- For patients who develop diarrhea during Cycle 1, loperamide should be increased up to a maximum of 16 mg a day.
- If a patient is unable to tolerate loperamide due to symptomatic constipation, loperamide should be held until after the first bowel movement and then resumed at a dose reduced by one level from their current level.
- For recurrent symptomatic constipation events, hold loperamide until after the first bowel movement and then resume at a dose reduced to the next lower dose level.
- If a patient is unable to tolerate once-daily loperamide due to constipation, hold loperamide and discuss subsequent loperamide dosing with the Investigator or suitably trained and qualified delegate.
- Neratinib dosing should continue if loperamide is held.

Recommended dose reductions for loperamide are listed in the table below.

Loperamide Dose Reduction Levels for Constipation.

Dose Level	Loperamide Dose	Tablets/Capsules per day
0	4 mg TID	6 tablets/capsules a day
-1	4 mg BID	4 tablets/capsules a day
-2	2 mg TID	3 tablets/capsules a day
-3	2 mg BID	2 tablets/capsules a day
-4	2 mg once a day	1 tablet/capsule a day

Abbreviations: BID = twice daily; mg=milligrams; TID= three times daily.

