5.4.3.3 Additional Anti-Diarrheal Instructions

Treatment of diarrhea (Days 1-28)

- Follow dietetic measures:
 - Stop all lactose-containing products.
 - Drink 8 to 10 large glasses of clear liquids per day.
 - Eat frequent small meals.
 - Recommend low fat regimen enriched with bananas, rice, applesauce and toast until resolution of diarrhea.
- For patients with persistent Grade 1 diarrhea (<4 stools per day above baseline) despite maximal loperamide use, Lomotil® (diphenoxylate hydrochloride and atropine sulfate) 1 tablet (2.5 mg) every 6 to 8 hours may be added (or equivalent).
- For Grade 2 diarrhea during the first 28 days (4 to 6 stools per day above baseline, despite intensive anti-diarrheal therapy), consider adding octreotide (short-acting) 150

- µg subcutaneous [SC] injection 3 times a day, or after initial dose of short-acting octreotide, if well tolerated, a single dose of octreotide LAR 20 mg by intramuscular (IM) injection (or equivalent).
- After resolution of diarrhea, loperamide prophylaxis can be decreased in 2-mg decrements with the goal of titrating to 1-2 bowel movements a day.

For new onset uncomplicated Grade 1 or Grade 2 diarrhea (>28 Days and beyond)

Dietetic measures

- Stop all lactose-containing products.
- Drink 8 to 10 large glasses of clear liquids per day.
- Eat frequent small meals.
- Recommend low fat regimen enriched with bananas, rice, applesauce and toast until resolution of diarrhea.

Pharmacological Treatment

- Administer loperamide: initial dose of 4 mg (2 tablets/capsules) with the first bout of diarrhea followed by 2 mg (1 tablet/capsule) every 4 hours or after every unformed stool (maximum 16 mg a day) and continue loperamide at this frequency until diarrhea free for 12 hours.
- For patients with persistent Grade 1 diarrhea on a maximum dose of loperamide (16 mg per day) Lomotil (diphenoxylate hydrochloride and atropine sulfate) 1 tablet (2.5 mg) every 6 hours to 8 hours may be added (or equivalent).
- For Grade 2 diarrhea during the first 28 days of treatment (4 to 6 stools per day above baseline, despite intensive antidiarrheal therapy), consider adding octreotide (short acting) 150 µg SC TID; or after initial dose of short-acting octreotide, if well tolerated, a single dose of octreotide LAR 20 mg IM (or equivalent medication).

For Grade 3 or Grade 4 diarrhea with complicating features (dehydration, fever, and/or Grade 3-4 neutropenia)

Dietetic measures (same as above)

Pharmacologic treatment

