- Administer loperamide: initial dose of 4 mg (2 tablets/capsules) with the first bout of diarrhea followed by 2 mg (1 tablet/capsule) every 4 hours or after every unformed stool (maximum 16 mg a day) and continue loperamide at this frequency until diarrhea free for 12 hours. Then titrate the amount of loperamide used to keep diarrhea controlled (<4 stools/day).
- Administer octreotide (100-150 µg SC BID or intravenously (IV) (25-50 µg/h) if dehydration is severe, with dose escalation up to 500 µg SC TID).
- Use IV fluids as appropriate.
- Consider prophylactic antibiotics as needed (e.g., fluoroquinolones) especially if diarrhea is persistent beyond 24 hours or there is fever or Grade 3-4 neutropenia.
- Stool cultures should be done to exclude infectious causes of Grade 3 or 4 diarrhea or diarrhea of any grade with complicating features (dehydration, fever, and/or Grade 3 or 4 neutropenia) per the Investigator's discretion. Results from occult blood, fecal

- leukocyte stain, Clostridium difficile, Campylobacter, Salmonella, and Shigella testing, when performed, should be recorded in the clinical records.
- Patients with significant diarrhea who are unresponsive to medical treatment may require treatment interruption or dose reduction.

Patient instructions for the management of diarrhea are provided in Appendix C.

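### Table 2's loperamide instruction after resolved diarrhoea is not reconciled with the Cycle 1 prophylaxis schedule, and one Grade 2 octreotide bullet sits where it cannot apply

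*Combined protocol and SAP*

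**What the plan says.** **Table 2 (Section 6.1.2).** The continue-neratinib row and the hold-neratinib row end with the same instruction. When the event has resolved to Grade ≤1 or baseline, the site is to "start loperamide 4 mg with each subsequent neratinib administration". Neither row gives a day or cycle limit. The first row covers Grade 1 diarrhoea as well as short-lived Grade 2 and Grade 3.

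**Neratinib frequency (Section 5.4.1).** "Neratinib is administered orally once daily, continuously with no breaks".

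**Prophylaxis schedule (Sections 5.4.3 and 5.4.3.1).** "Primary prophylactic use of antidiarrheal medication is mandatory for all patients taking neratinib". Loperamide is 4 mg three times a day for 14 days, then 4 mg twice a day "through the first cycle of therapy (Day 28) from start of neratinib dosing, whether the patient is experiencing diarrhea or not". If diarrhoea develops in Cycle 1, the dose is raised, up to 16 mg/day. After Day 28 it is given as needed at the investigator's discretion, with the same maximum.

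**After resolution (Section 5.4.3.3, text for Days 1-28).** "After resolution of diarrhea, loperamide prophylaxis can be decreased in 2-mg decrements", titrated to bowel movements.

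**Regimen table (Section 5.1).** "Loperamide: Days 1-28, continuous", against a 28-day cycle. The fulvestrant entry in the same table separates Cycle 1 from later cycles; the loperamide entry does not.

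**Octreotide (Section 5.4.3.3).** Under the heading for new-onset diarrhoea after Day 28, one bullet begins "For Grade 2 diarrhea during the first 28 days of treatment (4 to 6 stools per day above baseline, despite intensive antidiarrheal therapy" and suggests considering 150 µg subcutaneously three times a day. For Grade 3-4 diarrhoea with complicating features, the text begins "Administer octreotide (100-150" µg subcutaneously twice a day. It also gives an intravenous option of 25-50 µg/h for severe dehydration, and escalation up to 500 µg subcutaneously three times a day.

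**The concern.** A patient in Cycle 1 is already on mandatory loperamide, so an instruction to *start* it does not describe her situation. The same event is also covered by the step-down rule in Section 5.4.3.3. Two sites could treat the same patient differently after the same episode, each with protocol text to support it.

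Section 5.4.3 calls diarrhoea the major dose-limiting toxicity of neratinib, with onset typically in the first days of Cycle 1. Table 2 is where a site looks when it occurs, because it also decides whether neratinib is continued or held. At stake are the consistency and clarity of a safety instruction that applies equally to both arms.

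The octreotide bullet is a simpler problem. Its own time limit rules out the period named in its heading, so that part of the text has no working octreotide instruction for Grade 2.

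**Working it through.** **1. The plan's own totals (Section 5.4.3.1).** Daily total = dose × frequency.
- Days 1-14: 4 mg × 3 = 12 mg/day, as stated.
- Days 15-28: 4 mg × 2 = 8 mg/day, as stated.
- Maximum: 16 mg/day.

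**2. Table 2 total.** 4 mg per neratinib dose × 1 dose per day = 4 mg/day.

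**3. How the two combine.** Table 2 does not say, and three readings are open:

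| Reading of the 4 mg | Patient on 12 mg/day | Patient on 8 mg/day | Patient raised to 16 mg/day |
|---|---|---|---|
| Replaces the schedule | 4 (4/12 = 33%) | 4 (4/8 = 50%) | 4 (4/16 = 25%) |
| Added to the schedule | 12 + 4 = 16 | 8 + 4 = 12 | 16 + 4 = 20, above the maximum |
| Is one of the scheduled doses | 12 | 8 | 16 |

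**4. Against the step-down rule.** From 16 mg/day, the first step allowed by Section 5.4.3.3 is 16 − 2 = 14 mg/day. Reaching 4 mg/day would take (16 − 4)/2 = 6 steps. The two rules therefore agree only if Table 2's 4 mg is read as part of the existing dose.

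**5. Trigger.** Resolution is defined as Grade ≤1 or baseline. The first row includes Grade 1, so a patient with Grade 1 diarrhoea meets the trigger at onset.

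**6. After Day 28.** Section 5.4.3.1 says as needed. Section 5.4.3.2 leaves prophylaxis beyond Cycle 1 to the provider. Table 2 ties loperamide to every later neratinib dose, and the Section 5.1 table shows continuous use through a 28-day cycle without naming Cycle 1. No fixed doses conflict here, but the passages differ on whether loperamide is daily or as needed.

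**7. Cross-reference.** Table 2's lead-in sends the reader to Section 5.3.3 for dietary and drug treatment. Section 5.3 contains only 5.3.1 and 5.3.2; the diarrhoea rules are in 5.4.3. The same reference appears in the Section 5.1 table, in Section 5.4.1 and in the study calendar.

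**8. Octreotide daily totals (Section 5.4.3.3).**
- Grade 2, subcutaneous: 150 × 3 = 450 µg/day.
- Complicated Grade 3-4, starting subcutaneous dose: 100 × 2 = 200 to 150 × 2 = 300 µg/day, which is 200/450 = 44% to 300/450 = 67% of the Grade 2 total.
- Complicated Grade 3-4, intravenous: 25 × 24 = 600 to 50 × 24 = 1,200 µg/day.
- Complicated Grade 3-4, escalated subcutaneous: up to 500 × 3 = 1,500 µg/day.

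**The case against.** The strongest reply is that Table 2 was not meant to stand alone. Its title concerns neratinib dose adjustment, Section 6 calls its instructions guidelines, and the same rows tell the site to adjust anti-diarrhoeal treatment under the diarrhoea guidelines. Section 5.4.3.1 gives the first loperamide dose together with neratinib, so the 4 mg may simply be one of the scheduled doses. The patient sheet in Appendix C repeats the three-times-daily then twice-daily schedule and has no once-daily step. The 16 mg maximum appears in several places, and the step-down in Section 5.4.3.3 is permissive. After Day 28, *start* makes sense for a patient who has stopped loperamide.

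Much of this stands. A reader might infer that Table 2 cuts prophylaxis by 67% or 50%, but that follows only if the dose replaces the schedule, which Table 2 does not say. The 20 mg figure needs both the additive reading and a patient still on 16 mg. The schedule is itself adjustable: it can be lowered for constipation and changed at the provider's discretion if poorly tolerated.

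The reply does not remove the defect. The harmless reading has to be supplied by the reader, and the lead-in that should connect the table to the guidelines points to a section that does not exist. The provider discretion in Section 5.4.3.2 concerns trouble tolerating the drugs, not resolved diarrhoea. Appendix C's silence on the Table 2 rule leaves patient and site with different texts.

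A reader might also call the octreotide ladder inverted. Only the starting subcutaneous totals run that way; the intravenous and escalated options for Grade 3-4 exceed the Grade 2 total.

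**Conclusion.** The anti-diarrhoeal instructions are internally inconsistent as written and should be corrected. For a Cycle 1 patient whose diarrhoea has resolved, Table 2 can be read as 4 mg/day, as 12 to 20 mg/day, or as no change, depending on an unstated relation to the schedule. The misplaced octreotide bullet and the wrong cross-reference are plain errors and need no assumption. The lower starting subcutaneous octreotide total for complicated Grade 3-4 than for Grade 2 may be intended, and needs only confirmation.

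Three further inferences are not supported:
- **Number of patients affected.** A reader might apply the 95.4% any-grade diarrhoea rate in Table 5 to the sample size. That table's Grade 3 rate of 39.8% lies at the top of the 26-40% range that Section 7.1.1.2 gives for studies without prophylaxis, so the rate probably does not describe patients on prophylaxis. It is also not limited to Cycle 1.
- **Risk of severe diarrhoea.** The 11-28% and 26-40% Grade 3 ranges compare loperamide prophylaxis with none. They do not compare 4 mg with 8 or 12 mg/day.
- **Progression-free survival.** Neratinib and anti-diarrhoeal instructions are the same in both arms, and nothing in the documents yields a between-arm bias. The sample size, power and alpha do not depend on this point.

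**What to change.** The sponsor should reconcile the Section 5.1 table, Sections 5.4.3.1 and 5.4.3.3, and both rows of Table 2, choosing all doses itself:
- State one loperamide instruction after resolution for Cycle 1 and one for after Day 28.
- Say whether the Table 2 dose replaces, adds to or forms part of the prophylaxis schedule, and how it relates to the 16 mg maximum.
- Say how the Table 2 trigger applies to an event that is Grade 1 from the start.
- State in the Section 5.1 table which cycles the loperamide entry covers.
- Correct the reference to Section 5.3.3 wherever it appears.
- Correct the time limit or the placement of the Grade 2 octreotide bullet.
- Confirm that the starting octreotide doses for Grade 2 and complicated Grade 3-4 are as intended.
- Check Appendix C against the result.

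The cost is a wording amendment with its usual ethics review and a memo to sites. It adds no procedures, visits or data collection and does not touch the statistical design.
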